11.2.1. Efficacy analyses	
11.2.2. Safety analyses	
11.2.3. Additional analyses	
11.2.4. The level of significance	
11.2.5. Analysis Population.....	
12. Direct access to source data/documents	
13. Ethical considerations	
14. Data handling and keeping	
15. Financing and Insurance	

16. References.....

1. Synopsis

Protocol Title :
The role of migraine prophylaxis agent in treating patients with sudden sensorineural hearing loss – A randomized controlled trial
Study Objectives :
To understand the efficacy of migraine prophylaxis agent “topiramate” in treating patients with sudden sensorineural hearing loss
Investigational product(s) :
Topiramate
Development Phase :  I  II  III  IV  others _____ V not applicable
Study Design :
1. v Experimental Group v Control Group :  Placebo  Study Drug (Name , Dose , Usage) _____ v Other _standard systemic steroid with/without intratympanic steroid_
2. Blinding : v Open  Evaluator-blind  Single-blind(patient)  Double-blind(patient+PI)  Double Dummy  Other _____
3. Randomization: v Yes  No
4.  Parallel design  Crossover design  Other _____ v Not applicable
5. Treatment Period : _____ 6 weeks _____  Not applicable
6. Study Period: _____ 1 _____ year (or From DD/MM/YYYY to DD/MM/YYYY)
6. Dose adjustment : v Mandatory  Selectively  No  Not applicable
7. Study location :  Single v Multi-center  Global
Endpoints (Outcome measure) :
1. Primary endpoint: The improvement rate and gain of pure tone audiometry (compare day 0 and day 84)
2. Secondary endpoints: The improvement rate and gain of word recognition score (compare day 0 and day 84) The improvement rate and gain of pure tone audiometry (compare day 0 and day 56)
3. Exploratory endpoints (if any): nil
Inclusion/Exclusion Criteria :
Inclusion criteria
1. Age > 20
2. Confirmed diagnosis of unilateral sudden sensorineural hearing loss(SSNHL)
3. Treatment started 14 days within onset of SSNHL
Exclusion criteria
1. Previous SSNHL history

- 2. Previous middle ear disorder such as chronic otitis media, or previous ear surgery
- 3. Meniere's disease and fluctuating hearing loss patients
- 4. Pregnancy or trying to become pregnant
- 5. Leukemia, hemodialysis, and patients who received chemotherapy before.
- 6. Previous head and neck radiotherapy
- 7. Cerebellopontine (CP) angle tumor such as vestibular schwannoma
- 8. Patients with moderate to severe hepatic insufficiency
- 9. Patients with major depression disorder or suicide attempt
- 10. Patients with glaucoma

Study Procedures :

1. Expected inclusion patient number (enrolled number: **140**; evaluable number: **112**)
The participants would be divided into two group, half in the experimental group and the other half in the control group.
2. All patients will receive audiology examination, laboratory examination, magnetic resonance imaging of brain or auditory brainstem response at the first visit. Then the patient would be followed at the clinic weekly till the sixth week. Audiology examination will be arranged during the first week and then monthly till 12 weeks.
3. As for the treatment, the control group will receive systemic steroid with/without intratympanic steroid for 2 weeks as the standard therapy for sudden sensorineural hearing loss. The experimental group will receive systemic steroid with/without intratympanic steroid for 2 weeks and simultaneously oral topiramate for 6 weeks.
4. There will be no specimen collection in this study.
5. The patients' gender, age, initial and final hearing threshold, laboratory examination result, audiology result and symptoms will be collected.

Concomitant Treatments : not applicable

1. Concomitant Therapy : Prescribe systemic steroid with/without intratympanic steroid
2. Prohibited Therapy : nil

Statistical Methods :

1. Main study Hypothesis : Equality Superiority Non-inferiority
 Equivalence Other _____
2. Estimated Sample Size : Anticipated enrolled size 140 , Estimated evaluable number 112
Anticipated enrolled size in our center 45 , Estimated evaluable number in our center 40

Protocol: The role of migraine prophylaxis agent topiramate in treating patients with migraine and sudden sensorineural hearing loss

Version: 6

Date: 20220812

PASS 15.0.13

2022/8/2 下午 02:01:50

Two-Sample T-Tests Assuming Equal Variance

Numeric Results for Two-Sample T-Test Assuming Equal Variance

Alternative Hypothesis: $H1: \delta = \mu_1 - \mu_2 \neq 0$

Target Power	Actual Power	N1	N2	N	μ_1	μ_2	δ	σ	Alpha
0.80	0.80630	56	56	112	12.0	19.0	-7.0	13.0	0.050

References

Julious, S. A. 2010. Sample Sizes for Clinical Trials. Chapman & Hall/CRC. Boca Raton, FL.
Chow, S. C., Shao, J., and Wang, H. 2008. Sample Size Calculations in Clinical Research (Second Edition). Chapman & Hall/CRC. Boca Raton, FL.
Zar, Jerrold H. 1984. Biostatistical Analysis (Second Edition). Prentice-Hall. Englewood Cliffs, New Jersey.

Report Definitions

Target Power is the desired power value (or values) entered in the procedure. Power is the probability of rejecting a false null hypothesis.

Actual Power is the power obtained in this scenario. Because N1 and N2 are discrete, this value is often (slightly) larger than the target power.

N1 and N2 are the number of items sampled from each population.

N is the total sample size, $N1 + N2$.

μ_1 and μ_2 are the assumed population means.

$\delta = \mu_1 - \mu_2$ is the difference between population means at which power and sample size calculations are made.

σ is the assumed population standard deviation for each of the two groups.

Alpha is the probability of rejecting a true null hypothesis.

Summary Statements

Group sample sizes of 56 and 56 achieve 80.630% power to reject the null hypothesis of equal means when the population mean difference is $\mu_1 - \mu_2 = 12.0 - 19.0 = -7.0$ with a standard deviation for both groups of 13.0 and with a significance level (alpha) of 0.050 using a two-sided two-sample equal-variance t-test.

*Missing rate =10%, thus the enrollment size is 112/0.9=125

*Missing rate =20%, thus the enrollment size is 112/0.8=140

3. Efficacy assessment group : V Intent-to-treat (ITT) Per-Protocol (PP)
 Other _____
4. Interim analysis : Yes V No
5. Statistical methods : t test will be performed to compare pre- and posttreatment audiometric measurements. Chi-square and independent sample t test will be used to compare categorical and numerical variables between the two groups, respectively.
6. Handling of Missing Data : The cases with missing data will be omitted. The remaining data will be analyzed to determine the efficacy of study drug.

2. Introduction and Rationale

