2.5 Regulatory

This study will be conducted in compliance with the protocol approved by the Institutional Review Board, and according to Good Clinical Practice standards. No deviation from the protocol will be implemented without the prior review and approval of the IRB except where it may be necessary to eliminate an immediate hazard to a research subject. In such case, the deviation will be reported to the IRB as soon as possible.

3. Objectives and Endpoints

Objectives	Endpoints
Primary	
1.To understand the treatment effects of Topiramate for sudden sensorineural hearing loss	1.Pure tone audiology improvement (day 0 and day 84)
Secondary	
1.To understand the additional treatment effects of topiramate for sudden hearing loss events	1. word recognition score improvement (compare day 0 and day 84) 2. The improvement rate and gain of pure tone audiology (compare day 0 and day 56)

4. Study Design

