6.2. Concomitant Therapy

Both experimental group and control group will receive systemic steroid with/without intratympanic steroid as the standard treatment for sudden sensorineural hearing loss.

Hyperbaric oxygen therapy, a common therapy for sudden sensorineural hearing loss, is also allowed in these patients.

7. Efficacy Assessments

The evaluation of hearing ability is performed by pure tone audiometry, speech audiometry and word recognition test(WRS).

The audiometry will be arranged during the first clinic visit and followed at day 56 and day 84. Then the differences of the pre- and posttreatment audiometry will be evaluated.

The pure-tone average(PTA) calculated using 0.5-, 1-, 2-, and 3-kHz air conduction thresholds. The WRS is presented as percentage. The treatment efficacy compares the difference of PTA and WRS before and after treatment.

8. Safety Assessments

The most frequent side effects of the study drug are mild disturbance in taste, appetite, and paresthesia of distal extremities. There are no major adverse events reported in previous clinical trials. Those symptoms will be monitored and recorded during each clinical follow-up (from the first clinic to the end of follow-up after 3 months).

9. Adverse event reporting

[name] will report SAEs to the IRB of Chang Gung Medical Foundation according to the Serious Adverse Event Reporting Procedures and Guidelines as posted in the Clinical Trials Resource on the website of Chang Gung Medical Foundation IRB. SAE reports to the IRB should include the following information when calling the Medical Monitor:

- Date and time of the SAE
- Date and time of the SAE report
- Name of reporter
- Call back phone number
- Affiliation/Institution conducting the study
- Protocol number

- Title of protocol
- Description of the SAE, including attribution to drug and expectedness

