9.2 Adverse event follow-up

All AEs, including lab abnormalities that in the opinion of the investigator are clinically significant, will be followed according to good medical practices and documented as such. Site staff should send follow-up reports as requested when additional information is available. Additional information should be entered on the IRB of Chang Gung Medical Foundation of SAE form in the appropriate format. Follow-up information should be sent to Chang Gung Medical Foundation IRB as soon as possible according to IRB's Serious Adverse Event Reporting Procedures and Guidelines.

10. Criteria for the termination of the trial

The trial can be ended before the planned end date because of evidence of adverse effects (harm), or likelihood of failing to reject the null hypothesis (futility)

11. Statistical Considerations

t test will be performed to compare pre- and posttreatment audiometric measurements. Chi-square and independent sample t test will be used to compare categorical and numerical variables between the two groups, respectively.

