11.1 Sample size Determination

The study will be powered to approximately 80% assuming a standard deviation of 13 at an alpha of 0.05. The number of patients required to observe a 5dB difference between the experimental group and control group is about 56 patients in each group if the superiority margin at 0.05. The total estimated patients number required is 112. Consider the patient with incomplete data and drop-out rate of 20%, the total estimated number of sample size is about 140.

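### The primary endpoint names two measures of day-84 PTA change, improvement rate and gain, without saying which decides; of the rules examined, the stated 5% alpha and 80.63% power hold together only if gain decides.

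*Protocol*

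**What the plan says.** The Synopsis, under Endpoints, lists as primary: "The improvement rate and gain of pure tone audiometry (compare day 0 and day 84". It uses the same pair of terms for a secondary endpoint: "The improvement rate and gain of word recognition score (compare day 0 and day 84". Section 3 has one primary item, "Pure tone audiology improvement (day 0 and day 84", which could mean either measure.

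The analysis plan (Synopsis, Statistical Methods; sections 11 and 11.2) gives each type of variable its own test: "Chi-square and independent sample t test will be used to compare categorical and numerical variables between the two groups, respectively". Section 11.2.4 sets p below 0.05 as the criterion, with no order, split or joint rule.

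The only sizing is the software output in the Synopsis: "Group sample sizes of 56 and 56 achieve 80.630% power to reject the null hypothesis of equal means". It assumes means of 12 and 19, SD 13 and a two-sided alpha of 0.05. No rate is assumed or powered anywhere.

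Some text leans towards gain. Section 7 says "The treatment efficacy compares the difference of PTA and WRS before and after treatment". Section 11.2.1 defines hearing recovery as a gain above 10 dB, but does not link that to the improvement rate.

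**The concern.** Two measures with two tests at 0.05 and no decision rule leave at least four readings open:

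1. Gain alone decides.
2. Gain is tested first, then the rate.
3. Either measure suffices.
4. Both are required.

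The stated error rate and power describe the first two. The third raises the chance of a false positive primary claim. The fourth lowers the chance of success below the planned level. The trial is open-label and the rate has no definition, so the deciding measure and the rate's cut-off could both be settled after the data are seen.

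**Working it through.** **Inputs.** 56 per arm, means 12 and 19, SD 13, two-sided 0.05 (Synopsis, Statistical Methods). 20% loss (Synopsis and section 11.1). Cut-off above 10 dB (section 11.2.1).

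**Assumptions.** Gains are normal, and the improvement rate is the share of patients whose gain exceeds a dB cut-off. The sizing output names no variable or unit. It is read as PTA gain in dB because section 11.1 speaks of dB.

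**1. The plan's own figure.** Noncentrality = 7 / (13 × √(2/56)) = 7 / 2.457 = 2.849, with 110 degrees of freedom. Exact noncentral t power is 0.8063, which matches the stated 80.630%. Enrolment is 112 / 0.8 = 140, as stated.

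**2. The rate implied by the same inputs.** Control: Φ((12 − 10)/13) = 0.561. Topiramate: Φ((19 − 10)/13) = 0.756. Simulated chi-square power with 56 per arm is 0.594 (0.519 with Yates' correction). A normal approximation gives 0.585.

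**3. Decision rules at the 10 dB cut-off.** 2,000,000 simulated trials per scenario; Yates-corrected values in brackets.

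| Scenario | t-test on gain | Chi-square on rate | Either | Both |
|---|---|---|---|---|
| No effect, common mean 12 | 0.050 | 0.046 (0.029) | 0.0750 (0.0633) | 0.0208 (0.0156) |
| No effect, common mean 19 | – | – | 0.0824 (0.0671) | 0.0183 (0.0131) |
| 12 versus 19 | 0.806 | 0.594 (0.519) | – | 0.571 (0.505) |

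Check on the first row: 0.050 + 0.046 − 0.021 = 0.075.

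Under the gain-first sequence, gain keeps 5% and 80.63%. The rate is then also confirmed in 57.1% (50.5%) of trials at 7 dB.

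**4. Sensitivity to the cut-off.** These cut-offs are not in the protocol; they only test whether the result depends on 10 dB.

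| Cut-off | Either: type I error, mean 12 | Both: power, 12 versus 19 |
|---|---|---|
| 15 dB | 0.0764 (0.0646) | 0.588 (0.521) |
| 20 dB | 0.0817 (0.0674) | 0.576 (0.512) |
| 30 dB | 0.0888 (0.0626) | 0.406 (0.308) |

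**5. Rules that share alpha.** Uncorrected chi-square, 400,000 simulated trials where simulation was used.

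- Each measure at 0.025: type I error is about 4.2%, exact power for gain 71.7%, and power for at least one about 74%. Gain at 0.025 needs 67 per arm for 80% power.
- Hochberg: power about 75.5%.
- Gain at 0.04 with rate at 0.01: power about 78%.
- Minimum p-value calibrated to exactly 5%: power about 78%.

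None reaches 80.63%.

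**6. The design difference.** Section 11.1 sizes the same 56 per arm on 5 dB: "The number of patients required to observe a 5dB difference between the experimental group and control group". Noncentrality = 5 / 2.457 = 2.035, and power is 0.5229. For 80% at 5 dB, 107 per arm gives 0.7997 and 108 gives 0.8034. That is 216 evaluable, or 216 / 0.8 = 270 enrolled.

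**The case against.** The strongest reply is that gain was plainly meant. The Synopsis heads the item as a single endpoint, section 3 has one primary item, section 7 speaks of differences, and the sizing is on means. The 80.63% is claimed only for a t-test of equal means, and that remains true whatever the decision rule. Testing order and responder definitions are often left to a statistical analysis plan. The either and both readings are not proposed by the protocol, and the figures for them depend on an inferred definition of the rate.

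Much of this is fair. The evidence does favour gain, and the fix therefore adopts it. The stated power is not false as a statement about one test. The sizes in the tables are conditional, and they do not apply if the rate means a continuous percentage recovery, a reading for which nothing was computed.

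It does not remove the point. Naming the primary endpoint is the protocol's task, and this protocol names two measures, the rate first. A lean towards gain elsewhere does not withdraw the rate.

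The conflicts over frequencies and over 5 or 7 dB are separate faults and add nothing to the error inflation. They matter here only because a single primary endpoint needs one definition and one design difference.

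**Conclusion.** The point holds. The protocol names two primary measures and does not say which decides. Its 5% and 80.63% stand together if gain is the sole primary or is tested first, and under none of the other rules examined.

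With normal gains, SD 13, 56 per arm and a rate defined as gain above 10 dB:

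- **Either suffices:** type I error 7.5% to 8.2% (6.3% to 6.7% with Yates' correction).
- **Both required:** power 57% (50.5%) at 7 dB.

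The direction does not rest on the cut-off. Adding a second requirement cannot raise power, and accepting a second route at 0.05 cannot lower type I error, which is bounded by 10%. The inflation is moderate and conditional; the ambiguity is certain and cheap to remove.

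**What to change.** - Name mean PTA gain from day 0 to day 84 as the single primary endpoint, in the same words in the Synopsis and section 3.
- Make the improvement rate secondary. Define it for PTA, saying whether it is the recovery of section 11.2.1, and separately for word recognition score. If a formal claim on it is wanted, test it at 0.05 only after gain is significant.
- Use one frequency set. Section 7 has "The pure-tone average(PTA) calculated using 0.5-, 1-, 2-, and 3-kHz air conduction thresholds", while section 11.2.1 replaces 3 kHz with 4 kHz.
- Reconcile the 5 dB of section 11.1 with the 7 dB of the Synopsis. Only 7 dB reproduces the stated power with 56 per arm.

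If 7 dB is kept, this is a change of wording, with no new data or patients, and 5% and 80.63% then hold with 112 evaluable. If 5 dB is the intended difference, 216 evaluable and 270 enrolled are needed. The price in either case is that the improvement rate can no longer carry a primary claim by itself.

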2.1 Investigational product(s)

Topiramate is an anticonvulsant agent with multiple mechanism. The ability of preventing migraine attack was demonstrated by previous randomized controlled trials. It is an oral tablet with well tolerability. When using this agent to prevent migraine, the dosage started from 25mg per day and could be titrated up to 100mg per day.

2.2 Animal and preclinical study data

Not applicable

2.3 Clinical data

Migraine and sudden sensorineural hearing loss(SSNHL) are two related disorder. Systemic steroid is usually used to treat SSNHL but the role of migraine prophylaxis medication remained unknown. Mehdi Abouzari et al. found a better improvement when combining topiramate and nortriptyline with steroid in a retrospective study. However, a prospective study with randomization is needed to elucidate the efficacy of these agents.

2.4 Risks / benefits Assessment

Topiramate is a safe medication that has been already used in treatment of migraine prophylaxis and seizure. The potential adverse effects of topiramate includes mild disturbance in taste, loss of appetite, paresthesia of distal extremities, and increase fetal oral cleft risk. Therefore, children, adolescents and pregnant women were excluded from this study.

The possible benefit from using topiramate in this study is the possible better audiology improvement.

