4.3 Schedule of Activities

Time-Event scheme(評估時程表):

Phase	Screening	Treatment					Follow-up	
Day	0	0	7	14	21	28	56	84
Clinic visit	X	X	X	X	X	X	X	X
Screening/administration/safety								
ICF/assent form	X							
Inclusion/Exclusion criteria	X							
Medical and surgical history	X							
Lab exam	X							
MRI or ABR exam	X							
Randomization/Administration								
Randomization	X							
Administration of study drug	X	X	X	X	X	X		
Efficacy/Safety								
Symptoms			X	X	X	X	X	
Audiometry	X						X	X

The physician confirm that the patient meets the inclusion criteria at the initial visit (day 0). Then the patients would be asked if he/she is willing to participate into this clinical trial. If the patient agreed, then medical history taking, audiometry and lab examination, MRI or ABR examination will be arranged at same time. He/she will be randomized into either experimental arm or control arm. The treatment will be started immediately. The blood test will be performed at first visit and the data will be checked at day 7. Patients in both arms would follow up at our clinic at day 7,14,21,28,56, and 84. Pure tone audiometry and speech audiometry will be followed at day 56 and 84. Symptoms and adverse effects (safety monitoring) will be followed up at day 7,14,21,28, and 56.

5. Study Population

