5.2 Exclusion Criteria

Exclusion criteria:

- (1) Previous SSNHL history
- (2) Previous middle ear disorder such as chronic otitis media, or previous ear surgery
- (3) Meniere's disease and fluctuating hearing loss patients
- (4) Pregnancy or trying to become pregnant
- (5) Leukemia, hemodialysis, and patients who received chemotherapy before.
- (6) Previous head and neck radiotherapy
- (7) CP angle tumor such as vestibular schwannoma
- (8) Patients with moderate to severe hepatic insufficiency
- (9) Patients with major depression disorder or suicide attempt
- (10) Patients with glaucoma

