5.3 Withdrawal criteria

Withdraw from the study:

Participants of this study can withdraw from this study at any time when the patient disagree the consent, or had intolerable adverse effects after medication, or could not follow the treatment protocol.

The data of the withdraw patients will be excluded from the audiology analysis. The reason of withdrawal would be analyzed and reported.

6. Treatments

6.1.Treatment Administration

Both experimental group and control group will receive systemic steroid with/without intratympanic steroid as the standard treatment for sudden sensorineural hearing loss. The total duration of systemic steroid is 2 weeks.

As for the experimental group, topiramate 25 mg orally before bedtime with weekly escalation of 25 mg up to 100 mg. More specifically, the patient will receive 25mg daily at first week. Then the dose will be titrated up to 50mg in the second week, 75mg in the third week, and 100mg daily during the 4-6 weeks.

The dose of topiramate will be half in patients with renal insufficiency ($\text{Cl}_{\text{CR}} \leq 70 \text{ mL/min}$).

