9.1 Definitions and reports of Adverse Events

All adverse events that occur after the informed consent is signed (including run-in) must be recorded on the adverse event CRF (paper and/or electronic) whether or not related to study agent. AE Data Elements including:

- AE reported date
- AE Verbatim Term
- CTCAE Term (v 5.0)
- Event onset date and event ended date
- Severity grade
- Attribution to study agent (relatedness)
- Whether or not the event was reported as a Serious Adverse Event (SAE)
- Action taken with the study agent
- Outcome of the event
- Comments

Identify the adverse event using the NCI Common Terminology Criteria for Adverse Events (CTCAE) version 5.0. The CTCAE provides descriptive terminology and a grading scale for each adverse event listed.

AEs will be assessed according to the CTCAE grade associated with the AE term. AEs that do not have a corresponding CTCAE term will be assessed according to their impact on the participant's ability to perform daily activities as follows:

Grade	Severity	Description
1	Mild	
• Barely noticeable, does not influence functioning• Causing no limitations of usual activities
2	Moderate	
• Makes participant uncomfortable, influences functioning• Causing some limitations of usual activities
3	Severe	
• Severe discomfort, treatment needed• Severe and undesirable, causing inability to carry out usual activities
4	Life threatening	
• Immediate risk of death• Life threatening or disabling
5	Fatal	
• Causes death of the participant

The possibility that the adverse event is related to study drug will be classified as one of the following: not related, unlikely, possible, probable, definite.

DEFINITION of Serious Adverse Events: ICH Guideline E2A and GCP of Taiwan define serious adverse events as those events, occurring at any dose, which meet any of the following criteria:

- Results in death

- Is life threatening (Note: the term life-threatening refers to an event in which the patient was at risk of death at the time of the event; it does not refer to an event which hypothetically might have caused death if it were more severe).
- Requires inpatient hospitalization or prolongation of existing hospitalization
- Results in persistent or significant disability/incapacity
- Is a congenital abnormality/birth defect

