- Events that may not meet these criteria, but which the investigator finds very unusual and/or potentially serious, will also be reported in the same manner.

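### The fetal oral cleft risk named for topiramate is controlled only by an entry exclusion: no pre-dose pregnancy test is named, and no rule requires stopping, reporting or follow-up to outcome

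*Protocol*

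**What the plan says.** Section 2.4 lists the expected adverse effects of topiramate and ends with the fetal one, giving the entry exclusion as the response: "increase fetal oral cleft risk. Therefore, children, adolescents and pregnant women were excluded from this study". The matching criterion, in the Synopsis and as item (4) of Section 5.2, is "Pregnancy or trying to become pregnant". Section 5.1 sets a minimum age and no restriction by sex, so women able to conceive who are not trying to do so can enter.

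The Section 4.3 table has a day-0 laboratory entry without listing analytes. The text below it says: "The treatment will be started immediately. The blood test will be performed at first visit and the data will be checked at day 7". Safety contacts are then fixed: "Symptoms and adverse effects (safety monitoring) will be followed up at day 7,14,21,28, and 56". Section 8 carries symptom monitoring on to the end of follow-up at 3 months, but the effects it lists are taste, appetite and paresthesia.

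Section 5.3 lets a participant withdraw at any time if she no longer consents, or if she "had intolerable adverse effects after medication, or could not follow the treatment protocol". Section 6.1 sets six weeks of topiramate rising to 100 mg daily, and its only rule for departing from that schedule is "The dose of topiramate will be half in patients with renal insufficiency".

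Section 9.1 includes among the criteria for a serious adverse event "Is a congenital abnormality/birth defect", and adds that other events the investigator finds very unusual or potentially serious "will also be reported in the same manner". Section 9.2 has adverse events followed by good medical practice, with further reports as information arrives.

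**The concern.** An exclusion at entry deals with a pregnancy that is known on day 0. It does not deal with one that is present but unrecognised, or with conception during the six weeks of dosing. The protocol names the hazard itself, so one would expect it to say how pregnancy status is established before the first dose, what happens to the drug if pregnancy is confirmed, and who records the outcome. The visible text does none of these.

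The stake is patient safety. An unrecognised pregnancy could be exposed from day 0, and the outcome that Section 2.4 is concerned with could go unrecorded. No later analysis can recover an outcome that nobody collected.

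**Working it through.** The protocol gives no figure on this point to reproduce. The check sets the provisions against the three situations, then sizes the problem on stated assumptions.

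**Provisions against situations**

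| Situation | What the visible protocol provides | What is not there |
|---|---|---|
| Pregnant at entry, known | Exclusion (4) | – |
| Pregnant at entry, unrecognised | Eligibility check on day 0, method not stated; dosing the same day | A named test with the result read before dosing |
| Conception or recognition during dosing | Voluntary withdrawal (5.3); discretionary reporting (9.1) | A rule to stop topiramate; a rule that the pregnancy is reported |
| Outcome of an exposed pregnancy | Birth defect is a serious adverse event (9.1); adverse events followed by good practice (9.2) | A rule to follow the pregnancy to outcome after day 84 |

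**Time of birth against end of follow-up**

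Inputs: dosing from day 0 to day 42 (six weeks, Section 6.1); last visit day 84 (Section 4.3, and 12 weeks in the Synopsis); 266 days from conception to term (assumption).

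Days from last visit to term birth = conception day + 266 − 84.

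- Conception on day 0: 0 + 266 − 84 = 182 days.
- Conception on day 42: 42 + 266 − 84 = 224 days.

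A term birth after conception on drug therefore cannot fall within study follow-up. For a pregnancy that began d days before day 0, the figure is 182 − d. Its term birth is also after the last visit unless it was already more than 182 / 7 = 26 weeks from conception at entry.

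**Expected conceptions during dosing**

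Inputs: 140 / 2 = 70 assigned to topiramate (Synopsis, half per group); 42 days of dosing. Assumptions, not document figures: 10% to 40% of participants able to conceive, and 2% to 10% of those conceiving per year.

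Expected number = 70 × proportion able × yearly rate × 42 / 365.

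- Low: 70 × 0.10 × 0.02 × 42 / 365 = 0.016.
- Middle (25%, 6%): 70 × 0.25 × 0.06 × 42 / 365 = 0.12.
- High: 70 × 0.40 × 0.10 × 42 / 365 = 0.322.

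Chance of at least one (Poisson) = 1 − exp(−expected number).

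- Low: 1 − exp(−0.016) = 1.6%.
- High: 1 − exp(−0.322) = 27.5%.

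These figures leave out pregnancies already present but unrecognised on day 0, for which the protocol gives no basis. Expected clefts are fewer again, by a factor the protocol does not give.

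**Number of tests**

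Section 4.2 gives 140 enrolled, 28 drop-outs and 112 evaluable. Since 140 − 28 = 112, the 10 screen failures lie outside the 140, and 140 + 10 = 150 are screened. On the same 10% to 40%, that is 150 × 0.10 = 15 to 150 × 0.40 = 60 tests.

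**The case against.** The best case for the plan is that this is an argument from silence about a drug the clinicians already prescribe. Exclusion (4) can be checked on day 0 by history or a bedside test. A participant may withdraw at any time, Section 2.5 allows an immediate deviation to remove a hazard, and nothing tells anyone to continue topiramate in pregnancy. The consent pages were removed from the text under review and may contain contraception advice and a duty to tell the site.

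Much of this stands, and it rules out three stronger readings that a reader might infer.

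- *A pregnancy is not reportable.* The text does not support this. An investigator may judge a pregnancy on a drug with a named fetal risk to be potentially serious, and Section 9.1 then requires a report. The accurate statement is that no rule requires a pregnancy to be reported.
- *The pregnancy result is read only at day 7.* That holds only if a pregnancy test is part of the day-0 blood panel. The analytes are not listed, so the point is conditional.
- *The protocol keeps a pregnant participant on topiramate.* It does not say so; it is silent. Most clinicians would probably stop the drug.

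What the objection does not answer is the outcome. Section 9.2 has no day-84 cut-off, but it follows adverse events, and no text makes an uncomplicated pregnancy an adverse event. The birth-defect criterion works only if someone learns of a birth months after the last visit. Reliance on clinical judgement or a deviation also leaves handling to vary between the four hospitals. Whatever the consent pages say to participants, stopping and reporting rules belong in Sections 5.3, 6.1 and 9, which are present and do not contain them. A statistical analysis plan would not normally supply them.

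**Conclusion.** The point holds in a limited form. For a fetal risk that the protocol itself names, the only control in the visible text is the entry exclusion. No pre-dose test is named, and no rule requires topiramate to stop on confirmed pregnancy, the pregnancy to be reported, or its outcome to be followed after day 84.

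The frequency is low, with well below one conception on drug expected in the trial. The upper end of that range needs both high assumptions at once, in a population that excludes women trying to conceive. The timing result is firmer: it rests only on the dosing and visit days and an assumed 266 days to term. Sample size, power and the efficacy analysis are untouched. The change is worth making because the harm is serious, would be unrecoverable if missed, and costs little to guard against.

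**What to change.** 1. **Sections 4.3 and 5.2:** for women able to conceive, do a rapid pregnancy test at the day-0 visit and read it before the first dose. Reading it before randomisation is better still, so that the exclusion applies equally to both arms.
2. **Sections 5.3 and 6.1:** state that topiramate stops on confirmed pregnancy, with the manner of stopping for the sponsor to set, and that visits and audiometry continue to day 84. Stopping the drug should not count as withdrawal, because Section 5.3 removes withdrawn patients from the audiology analysis.
3. **Section 9:** state that any pregnancy during topiramate exposure is reported to the IRB and followed to outcome, including after day 84. One question about pregnancy at the existing visits would support this.

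The cost is a short amendment, about 15 to 60 inexpensive tests on the assumption above, a short wait before the first dose and, rarely, a record kept open past day 84. No visits are added.
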